### **Background, Rationale, and Context**

Despite advances in perinatal care in the U.S., maternal mortality has more than doubled over the past two decades, with substantial racial and socioeconomic disparities observed.[1] Hypertensive disorders of pregnancy (HDP) are a leading cause of perinatal morbidity and mortality, with up to 20% of maternal deaths attributed to preeclampsia.[2] In the traditional postpartum care model, many women are not seen for follow-up until six weeks postpartum, with the highest risk women typically scheduled for follow-up three to seven days after discharge. Thus, the postpartum period is a time of particular susceptibility for maternal morbidity and mortality resulting from undiagnosed or inadequately managed HDP.[3] Women from lower socioeconomic status (SES) groups, as well as racial and ethnic minority groups, disproportionately experience an increased risk for adverse consequences from HDP.[4] To mitigate this risk, the American College of Obstetrics and Gynecology (ACOG) recommends blood pressure monitoring (BPM) at 72 hours and through 7-10 days postpartum for women with HDP.[5]

Postpartum readmission for HDP is not limited to antenatally diagnosed HDP; women at “low-risk” account for a significant proportion of readmissions for HDP.[6] ACOG guidelines for postpartum care in lower-risk women recommend an initial postpartum visit by three weeks and a final comprehensive visit by 12 weeks postpartum.[7] However, the majority of readmissions for postpartum HDP occur prior to three weeks, suggesting that this care model is likely inadequate for many women and may contribute to missed or delayed diagnosis and treatment of HDP. In our own, highly diverse patient population, with nearly two-thirds of pregnancies covered by Medicaid or without insurance, compliance with recommended in-person, postpartum visits through this period, among women with higher and lower risk, is less than 50% (internal data).

Given the postpartum risks, women with known HDP experience increased length of stay during their initial postpartum admission.[8] While the increased length of stay has been associated with decreased readmission for HDP, it has also been associated with a significant increase in delivery hospitalization charges.[8] Remote BPM in the postpartum period has been proposed as an intervention to achieve increased monitoring without extending inpatient length of stay.[9]

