### **Sample Size**

It is estimated that approximately 5,000 women will deliver in Forsyth County over a 30 month time period. Of these, we anticipate that approximately 2000 women will be randomized equally (1000 in each study arm) during this time period.

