### **Feasibility and acceptability outcomes**

#### Primary:

Among those randomized to the intervention arm, at least 90% will have a smartphone and will be able to have the remote BPM app loaded onto their phone, prior to discharge. We hypothesize an absolute difference of no more than 10% (e.g., 85% vs 95% with a smartphone) according to insurance status (Medicaid or uninsured vs. private insurance).

Remote BPM will be successfully integrated into patient care as evidenced by at least 90% adherence to a median of at least one blood pressure reading/day for three weeks and 70% adherence to obtaining a median of two blood pressure measures for initial 2 weeks postpartum. We hypothesize an absolute difference in adherence, according to patient insurance status of <15%.

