## **Analytical Plan**

The subject will complete a baseline demographic questionnaire at the time of enrollment. This questionnaire will be completed electronically through a unique link via REDCap. Additionally, subjects in the rBPM study arm will be asked to complete a post-study questionnaire electronically through a unique link via REDCap ~ 1 week after subject has completed the study.

The following EHR-based clinical measures will be obtained from each subject:

- Demographics
- History of hypertension or use of blood pressure lowering agents
- Pregnancy-related data (e.g. blood pressure, pre-pregnancy BMI, weight gain, complications, pre-pregnancy diabetes, gestational diabetes, delivery complications)
- Birth outcomes, including gestational age at delivery, cesarean or vaginal delivery, singleton or multiparous delivery, birth weight
- Length of stay of admission and any readmissions through 12 weeks postpartum
- Use of blood pressure lowering agents through 12 weeks postpartum

We will link EHR, BP, baseline demographic questionnaire data, billing, and user satisfaction data to inform study questions as described above. Data will be reviewed for missingness, with multiple imputation performed as appropriate. Initially, data will be analyzed using descriptive statistics. Comparison between groups may be performed using chi square tests for proportions, and t-tests or ANOVA procedures for continuous variables. Crude and adjusted regression analysis will be performed to identify independent outcome predictors. Other inferential statistical analysis will be conducted as appropriate.

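### The primary feasibility hypotheses by insurance status are margin claims (15 and 10 points), but the only named test for proportions has a zero-gap null and no decision rule is stated

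*Combined protocol and SAP*

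**What the plan says.** The primary outcomes under Feasibility and acceptability outcomes, all within the remote-monitoring arm, contain two statements on insurance status.

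- **Smartphone and app.** The absolute gap is to be no more than 10 points, "according to insurance status (Medicaid or uninsured vs. private insurance"), with 85% against 95% given as an example.
- **Adherence.** There are two targets. The once-daily target is "at least 90% adherence to a median of at least one blood pressure reading/day for three weeks". The twice-daily target is worded as "70% adherence to obtaining a median of two blood pressure measures for initial 2 weeks postpartum". The insurance statement follows: "We hypothesize an absolute difference in adherence, according to patient insurance status of <15" percent. The groups are not redefined, so I take them to be the same.

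The Analytical Plan does not mention these limits. On comparing groups it says: "Comparison between groups may be performed using chi square tests for proportions, and t-tests or ANOVA procedures for continuous variables". It adds crude and adjusted regression to find predictors, and leaves room for other inferential methods. It gives no significance level, interval rule, equivalence or non-inferiority test, or success criterion for either limit.

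The secondary satisfaction outcome is worded differently, as an absence of significant difference by insurance. The protocol therefore uses two kinds of hypothesis, and the Analytical Plan does not separate them.

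**The concern.** To support a claim that a gap is below 15 points, the null to reject is a gap of 15 points or more. Chi-square tests a gap of exactly zero. A significant result does not mean that the gap reaches 15 points, and a non-significant one does not by itself bound it below 15.

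With no rule fixed, the same data can be read in three ways: by the chi-square p-value, by comparing the observed gap with the margin, or by a confidence interval against the margin. These can give opposite answers. The statements are labelled primary, and equity by socioeconomic group is a stated aim of the trial, so the choice of reading should not be left until the data are seen.

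**Working it through.** **The plan's own figure.** None is attached to these hypotheses. The Sample Size section expects that "approximately 2000 women will be randomized equally (1000 in each study arm"), a recruitment estimate with no significance level, power or effect size. There is nothing to reproduce.

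**Inputs.**
- Women with adherence data: 1,000, the remote-monitoring arm; 500 as a sensitivity case.
- Insurance split: 650 Medicaid/uninsured and 350 private. This is an assumption based on the Background, which describes the source population as having "nearly two-thirds of pregnancies covered by Medicaid or without insurance".
- Private-group adherence: 75% and 95%, assumed so as to bracket results near the 70% and 90% targets.
- Level: two-sided 0.05, assumed because none is stated.

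**Formulas.** Let d be the true gap (private minus Medicaid/uninsured), m the margin, s0 the pooled standard error and s1 the unpooled one.
- P(chi-square significant) ≈ Φ((d − 1.96·s0)/s1)
- P(upper 95% limit below m) ≈ Φ((m − 1.96·s1 − d)/s1)
- P(observed gap below m) ≈ Φ((m − d)/s1)

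**Worked case: 75% against 70%, d = 0.05, m = 0.15.**
- Pooled rate = (650 × 0.70 + 350 × 0.75)/1000 = 0.7175.
- s0 = √[0.7175 × 0.2825 × (1/650 + 1/350)] = 0.0298.
- s1 = √[0.70 × 0.30/650 + 0.75 × 0.25/350] = 0.0293.
- Chi-square significant: Φ((0.05 − 0.0585)/0.0293) = Φ(−0.29) ≈ 39%.
- Upper limit below 15 points: Φ((0.15 − 0.0574 − 0.05)/0.0293) = Φ(1.45) ≈ 93%.

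**Binomial simulation, 650/350, Wald interval, 15-point margin.**

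| Private rate | True gap | Chi-square significant | CI within ±15 | Observed gap <15 |
|---|---|---|---|---|
| 75% | 3 | 17% | 99% | >99% |
| 75% | 5 | 39% | 93% | >99% |
| 75% | 7.5 | 70% | 72% | 99% |
| 75% | 10 | 91% | 39% | 95% |
| 75% | 15 | 99.8% | 2.4% | 50% |
| 95% | 3 | 43% | >99% | >99% |
| 95% | 5 | 81% | >99% | >99% |
| 95% | 7.5 | 98% | 99% | >99% |
| 95% | 15 | >99% | 2.4% | 50% |

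In the row for 95% and 7.5 points, 97.5% of trials are both significant by chi-square and have an interval inside the margin. Such data would show a significant difference and also establish the protocol's hypothesis. A Newcombe interval changes the CI column by about 2 points at most.

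**Fewer women analysed (325/175), true gap 5.** Chi-square is significant in 21% (private 75%) and 50% (private 95%). The interval rule succeeds in 68% and 99%.

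**Anchored on the protocol's overall targets (667/333).** At a 5-point gap chi-square is significant in about 73% on the 90% endpoint and 37% on the 70% endpoint. It passes 50% at gaps of 3.9 and 6.0 points respectively.

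**Smartphone and app, 10-point margin.** At the protocol's own example of 85% against 95% (667/333), chi-square is significant in 99.9% of trials, although that gap is within the stated limit.

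**The case against.** The Analytical Plan does not assign chi-square to these hypotheses. Its wording is optional, it starts with descriptive statistics, and it allows other methods. A margin analysis is therefore unspecified, not excluded. This stands, and it makes the fault an omission.

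A reader might infer that the plan would usually report an accepted gap as a failure. The documents do not support this. Nowhere do they say that a significant chi-square refutes the margin hypothesis, and the different wording for satisfaction suggests that the authors did not mean a zero-gap comparison here. Nor does the word usually fit every case: chi-square is significant more often than not only for gaps above about 4 points (90% endpoint) or 6 points (70% endpoint), and then only at full enrolment.

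A reader might also infer that chi-square would let a true 15-point gap through. It would not: at full enrolment with private adherence at 75%, a non-significant result at that gap occurs in about 100 − 99.8 = 0.2% of trials. The 50% pass rate belongs to a different reading, the point estimate set against the margin. No single rule has both faults.

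Finally, the limits may be meant as descriptive feasibility benchmarks. That is a fair reading. At a true gap of 10 points, where the hypothesis is true, the point estimate passes in about 95% of trials against 39% for the interval (private 75%). But a benchmark passed half the time by a gap exactly at the limit is weak support for a primary claim, and the plan does not say that the limits are only descriptive.

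**Conclusion.** The point holds as a mismatch between the form of the hypotheses and the only test named for proportions, with no decision rule to bridge them. Chi-square cannot establish a gap below 15 or 10 points. That conclusion needs no assumption, and the roughly 50% pass rate at the margin under a point-estimate reading hardly depends on the inputs.

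The other magnitudes rest on an assumed split, private-group rates, significance level and number analysed. On those assumptions, a 5-point gap that the protocol accepts is significant in 39% to 81% of trials at 1,000 women and 21% to 50% at 500, and less often for smaller gaps. They show how far the possible readings diverge, not the error rate of a rule that the plan adopts.

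The change should be made: the hypotheses are labelled primary, and the planned arm can support the better analysis. At a true 5-point gap the interval rule succeeds in about 93% of trials or more for adherence at full enrolment.

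**What to change.** In the primary feasibility outcomes and the Analytical Plan, treat three endpoints separately: once-daily adherence over three weeks, twice-daily adherence over two weeks, and smartphone with app loaded. For each:

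- Report the risk difference between insurance groups with its two-sided 95% confidence interval (for example Newcombe or Miettinen-Nurminen), and state the analysis set.
- Call the hypothesis supported only if the whole interval lies within the margin (15 points for adherence, 10 for smartphone and app). Apply it in both directions, because the protocol gives an absolute difference and names no direction.
- Report separately whether the interval excludes zero, so that a small real gap inside the margin is described as such and not as a failure.

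The cost is a few sentences, with no new data or participants. The downside is a stricter standard: at a true 10-point adherence gap with private adherence at 75%, success falls to about 39%, against about 95% for the point estimate.

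For smartphone and app, the protocol's example of 85% against 95% lies exactly on the 10-point margin, where the rule succeeds in only about 2% to 3% of trials; at a true 5-point gap (90% against 95%, 650/350) it succeeds in about 86%. The team should therefore decide whether 10 points is the margin or the gap it expects. If any limit is meant only as a descriptive benchmark, the plan should say so and still give the interval.

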#### Secondary:

A high proportion (>90%) of patients indicating satisfaction with use of the remote BPM tool, with no significant difference in satisfaction according to patient insurance status. Satisfaction to be assessed at 3-4 weeks postpartum through a unique link to a satisfaction survey sent to participant.

### **Clinical outcomes**

#### Primary:

We anticipate a significant increase in proportion of women having their blood pressure monitored according to ACOG guidelines for obtaining BP measures (obtain BP with 72 hours of discharge and maintain monitoring through 7-10 days for all women with hypertensive disorders of pregnancy (HDP)), with an absolute difference of >30% between those randomized to usual care versus remote BPM for within 72 hours and an absolute difference of 30% for continuous monitoring through 10 days (60% for usual care vs 90% intervention arm in those with higher risk - antepartum/delivery HDM).

Among all women (with and without HDP) we anticipate an absolute difference of 60% between those randomized to usual care versus remote BPM for obtaining blood pressure measures within three weeks of discharge (30% usual care vs 90% intervention arm for low and high risk women combined). We hypothesize that the disparity in obtaining these measures, according to insurance status, will be reduced.

### Secondary:

Remote BPM will decrease the duration of stay in the postpartum unit, with women with remote BPM discharged earlier than those with usual care, with a median, absolute decrease of length of stay of >1 day(s), irrespective of insurance status.

### Secondary:

Readmissions for HDP, within eight weeks of discharge, occurs in ~2% of the general patient population.[4,8] We hypothesize an absolute decrease of 60% in readmission rates. With earlier intervention, we hypothesize that the median length of stay for the readmission will be significantly reduced in the intervention arm.

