After obtaining electronic consent via REDCap, the subject will be asked to complete a baseline demographic questionnaire (*Appendix 1a and 1b*). After this brief questionnaire is completed, the subject will then be randomized into one of two study arms; either rBPM or SOC. Study ID numbers will be assigned to each subject. Randomization assignment will be completed by a study staff member using the REDCap randomization tool after enrollment and after the subject has completed the baseline questionnaire in REDCap or in real time if the subject is enrolled in the hospital after delivery. All subjects have an equal chance of being assigned to either the rBPM or SOC study arm. The study arm assignment will be documented in the subject's EMR. The subjects that were enrolled during a prenatal clinic visit will not be aware of their study arm assignment until after they have delivered their infant(s) at The Birth Center. Logistically, it is not feasible to complete the randomization in real-time in the outpatient setting, and there are no study activities that occur between the time of the subject's outpatient prenatal clinic visit and their delivery at The Birth Center.

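### The readmission hypothesis is arithmetically impossible as written, and its companion length-of-stay comparison is confined to women selected by an event after randomisation

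*Combined protocol and SAP*

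**What the plan says.** Under Clinical outcomes, in the Secondary paragraph on readmissions, the protocol gives the base rate: "Readmissions for HDP, within eight weeks of discharge, occurs in ~2% of the general patient population". It continues: "We hypothesize an absolute decrease of 60% in readmission rates". The next sentence turns to duration: "we hypothesize that the median length of stay for the readmission will be significantly reduced in the intervention arm". Neither an intervention-arm readmission rate nor an effect size for the stay is given.

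Readmission and readmission length of stay (LOS) carry a secondary label there, but both are also listed under the Primary Objective and again in Outcome Measures.

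The Sample Size section expects that "approximately 2000 women will be randomized equally (1000 in each study arm") will be recruited. This is a projection from local deliveries, with no significance level, power or target effect. The Analytical Plan says "Comparison between groups may be performed using chi square tests for proportions" and names "t-tests or ANOVA procedures for continuous variables". It gives no method for medians and none for an outcome that exists only in readmitted women.

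**The concern.** There are two linked faults in the same paragraph.

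**The effect size.** An absolute fall of 60% cannot start from 2%. The word cannot be passed over as loose usage, because the Primary clinical outcome uses an absolute difference of 60% for "30% usual care vs 90% intervention arm for low and high risk women combined", which is 60 percentage points. As it stands, a reader cannot tell what reduction the investigators expect, or whether 1000 per arm is adequate to see it.

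**The stay.** Median LOS for the readmission is defined only for women who are readmitted. Readmission occurs after randomisation and is something remote monitoring is intended to change. The readmitted women in the two arms are therefore not groups formed by randomisation, and a difference in their stays could reflect who was readmitted, not how long comparable women stayed. The hypothesis nevertheless speaks of a significant reduction, and a reader of the results would take it as a treatment effect.

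**Working it through.** **Inputs.** Base rate about 2% (Secondary readmission paragraph); 1000 per arm (Sample Size); 1:1 allocation (Methods and Measures: "All subjects have an equal chance of being assigned to either the rBPM or SOC study arm"). Assumed, because the protocol does not state them: two-sided 5% level, no loss to follow-up, one readmission per woman.

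**1. The figure as written.** 2% − 60 points = −58%. The largest possible absolute fall is 2 points. The stated figure cannot be reproduced.

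**2. The two feasible readings.**
- 60% relative: 0.02 × 0.40 = 0.008, a fall of 1.2 points. Expected readmissions 20 + 8 = 28.
- 0.6 points: 0.020 − 0.006 = 0.014. Expected readmissions 20 + 14 = 34.
- For reference, no effect: 20 + 20 = 40.

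**3. Power for the readmission rate.** With d = p1 − p2 and p̄ = (p1 + p2)/2:

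SE0 = √[2p̄(1 − p̄)/n], SE1 = √[p1(1 − p1)/n + p2(1 − p2)/n], power = Φ[(d − 1.96·SE0)/SE1].

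- 2.0% v 0.8%: SE0 = 0.00525, SE1 = 0.00525; (0.012 − 0.0103)/0.00525 = 0.324; power = 62.7%. Exact enumeration gives 64.7% for the chi-square test and 56.3% for Fisher's test. The formula needs 1504 per arm for 80% power.
- 2.0% v 1.4%: SE0 = SE1 = 0.00578; (0.006 − 0.01133)/0.00578 = −0.922; power = 17.8%. For 80% power, 7286 per arm.

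Expected 95% CI on the relative reading: 0.012 ± 1.96 × 0.00525, or 0.2 to 2.2 points.

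The 2% is quoted for a general population, so it needs a range. With a 60% relative fall at 1000 per arm:

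| Base rate | Expected readmissions | Power |
|---|---|---|
| 1% | 10 + 4 = 14 | 36% |
| 2% | 20 + 8 = 28 | 63% |
| 3% | 30 + 12 = 42 | 80% |
| 4% | 40 + 16 = 56 | 90% |

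**4. Size of the LOS comparison.** With 20 v 8 stays, the detectable difference at 80% power is about (1.96 + 0.84) × √(1/20 + 1/8) = 1.17 SD, or 1.22 SD with the t distribution. Power is 21% at 0.5 SD and 63% at 1.0 SD. These are for a t-test on means and serve only as a guide to a comparison of medians.

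**5. Direction of bias.** Two illustrations with invented stays show that the sign is open.
- Usual care: 12 stays of two days and 8 of four (median 2, total 24 + 32 = 56 days). Monitoring prevents the 12 short ones, leaving 8 of four days (median 4, total 32). Bed-days fall by 24/56 = 43%, yet the median doubles.
- Usual care: 8 stays of two days and 12 of four (median 4, total 16 + 48 = 64 days). Monitoring detects more and adds 8 two-day stays, giving 16 of two days and 12 of four (median 2, total 32 + 48 = 80). The median halves, yet bed-days rise by 16/64 = 25%.

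A larger sample would not remove either distortion.

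**The case against.** The best defence is that nothing depends on the 60%. The outcome paragraph is headed secondary, the 2000 is a recruitment projection not derived from this effect, and no success criterion or analysis uses it. The comparison of readmission rates can be run unchanged. All of this stands, and it limits the seriousness of the point. Nor does the protocol claim that the readmission rate will differ significantly; only the LOS sentence uses that word. So moderate power contradicts no statement in the plan, though it should be disclosed.

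Three stronger readings are tempting and are not supported:
- *That a relative fall is the only possible meaning.* It is the likelier slip, but 0.6 points is also arithmetically possible and no other section settles the matter.
- *That the trial has 63% power for readmission and will yield 28 readmissions.* Both figures rest on the relative reading, a 2% base in this population and an assumed significance level. The cohort is described as highly diverse and largely on Medicaid or uninsured, so its rate may differ from 2%.
- *That monitoring will prevent the milder readmissions and so make the remaining stays look longer.* The documents do not say this. The alert pathway sends some women to an office visit or OB triage, which could instead add short admissions in the monitored arm.

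It can also be objected that readmission days per randomised woman mixes incidence with duration and no longer asks whether stays are shorter. That is true and is a real cost. But whether a readmitted woman stays less long because of the intervention is not a question that randomisation answers here.

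**Conclusion.** The point holds. The absolute 60% fall from about 2% is impossible and must be a slip, but its intended value is not recoverable from the document. The two feasible readings differ twofold in effect (1.2 v 0.6 points) and in power (about 63% v 18%), at 1000 per arm, two-sided 5% and no loss to follow-up. On the relative reading, power runs from 36% to 90% across base rates of 1% to 4%.

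The LOS hypothesis rests on about 28 to 40 readmitted women at a 2% base. They are selected by an event after randomisation that the intervention is meant to affect, so the comparison is not protected by randomisation, and the direction of any bias is unknown.

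This should be fixed, but it is not critical. A reader might infer that it undermines the trial's main conclusions; it does not, because the blood-pressure adherence outcomes neither use this figure nor condition on readmission.

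**What to change.** 1. The sponsor confirms the intended effect, and the protocol replaces the sentence with the expected readmission rate in each arm, stating the difference in percentage points and, if wanted, as a relative reduction.
2. State the significance level and the power of 1000 per arm over a plausible range of base rates, not as a single figure. Report the risk difference with its 95% CI.
3. Report LOS among readmitted women descriptively, with no test and no claim of significance.
4. Make the between-arm comparison on total readmission days per randomised woman to eight weeks after discharge, counting zero for women not readmitted, with a bootstrap interval or permutation test for the difference in means.

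**Cost.** Wording only. The Analytical Plan already collects readmissions and their length for every subject through 12 weeks postpartum.

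**Downside.** The new measure combines incidence and duration and is mostly zeros: with 28 readmissions in 2000 women, 1972/2000 = 98.6%. It may have no more power than the readmission rate itself. In simulations with 2.0% v 0.8% readmitted, equal mean stays and assumed lognormal stays, power was about 60% at a coefficient of variation of 0.3 and 42% at 1.0, against about 63% for the rate. It should be presented as an estimate with its interval.
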